## **10. DATA QUALITY ASSURANCE AND DATA MANAGEMENT**

### **10.1. Quality control and source data verification**

Source data verification will be conducted with due regard to subject confidentiality.

The clinical unit will allow the study monitor and sponsor representative direct access to all study documents, medical files, and source documents to enable verification of the study data, whilst maintaining the anonymity of the subject and confidentiality of the data.

Internal quality control will be performed at all stages of the study by the clinical unit.

### **10.2. Audit/Inspections**

The clinical unit facilities and all study data/documentation may be audited/inspected by independent auditor/inspector/any representatives of regulatory authorities. The investigator must allow the applicable persons access to all relevant facilities and data/documents. The investigator must be available to discuss any findings/issues.

If an audit was performed, the audit certificate will be included in the CSR.

### **10.3. Study monitoring**

The conduct of the study will be monitored by an independent PAREXEL monitor or a subcontracted monitor to ensure compliance with applicable regulatory requirements and GCP. The summary of the documentation of the monitoring visits will form part of the study documentation and will be archived as such.

### **10.4. Data collection**

PAREXEL's ClinBase system is an electronic source data capturing and information management system. The system combines all aspects of source data capturing with process control and clinical study management. All clinical and laboratory data, except those which are paper-based and/or transferred by external vendors, will be collected in ClinBase. Only paper-based data will be subject to data entry. For electronic source data, no data entry will be performed.

The responsible study monitor will check data at the monitoring visits to the clinical unit. The investigator will ensure that the data collected are accurate, complete and legible. Data will be monitored within ClinBase by the study monitor before being exported. Any changes made during monitoring will be documented with a full audit trail within ClinBase.

#### **10.4.1. Case report forms and source documents**

All data obtained using paper collection methods during the clinical study will be recorded in ClinBase. All source documents from which ClinBase entries are derived should be placed in the subject's personal records.

The original ClinBase entries for each subject will be checked against source documents by the study monitor. Instances of missing or uninterpretable data will be discussed with the investigator for resolution.

#### **10.4.2. Access to source documents**

During the course of the clinical study, a study monitor will make clinical unit visits to review protocol compliance, compare ClinBase entries and individual subject's personal records, assess IMP accountability and ensure that the clinical study is being conducted according to pertinent regulatory requirements. ClinBase entries will be verified against source documents. The review of medical records will be handled confidentially to ensure subject anonymity.

Checking of the ClinBase entries for completeness and clarity and verifying with source documents, will be required to monitor the clinical study for compliance with GCP and other regulations. Moreover, regulatory authorities of certain countries, IECs/IRBs may wish to carry out source data inspections on-site, and the sponsor's clinical quality assurance group may wish to carry out audits. Direct access to source data will be required for these inspections and audits; they will be carried out giving due consideration to data protection and subject confidentiality. The investigator assures the sponsor of the necessary support at all times.

#### **10.5. Data management**

PAREXEL will utilize standardized and validated procedures and systems to collect, process and file the clinical data of this study. Any system used will be compliant with FDA 21 CFR Part 11 requirements.

A data management plan (DMP) will be prepared to describe the processes and data-flow within the clinical study. Timelines, versions for the computer systems and the coding will be defined in the DMP, and if applicable, sponsor specific requests will also be documented within. The DMP will be finalized before first dose where possible but before database lock.

A data validation specification (DVS) will be created to outline the validation checks to be performed during the study. The DVS must be finalized before data validation.

After the data has been monitored by the responsible study monitor all data received will be reviewed, logged and filed.

The raw data intended for further processing will be checked by standard routines or according to the DVS and queries will be generated and sent to the investigator for review and resolution. Corrections resulting from these queries will be confirmed on the data clarification forms (DCFs). This process will be repeated until no further discrepancies are found. The data will then be declared as clean. Applicable documentation will be stored in the study files.

Only trained study staff will have access to the clinical database and every change in data will have a full audit trail.

## **11. STATISTICAL METHODS**

### **11.1. Overview**

The statistical methodology below describes the statistical analysis as it is foreseen when the study is being planned.

If circumstances should arise during the study rendering the analysis inappropriate, or if in the meantime improved methods of analysis should come to light, different analyses may be performed. A separate statistical analysis plan (SAP) will not be written for the study. Any deviations from the statistical methodology defined in this protocol, reasons for such deviations and all alternative/additional statistical analyses that may be performed will be described in the CSR. Such changes to analyses may be written into an abbreviated SAP, if appropriate. The verification and review of all statistical modelling assumptions will be documented appropriately.

### **11.2. General statistical methodology**

All original and derived parameters as well as demographic and disposition data will be listed and described using summary statistics. All safety data (scheduled and unscheduled) will be presented in the data listings.

Demographic and baseline data will be summarized by treatment sequence and overall. Pharmacokinetic data will be summarized by treatment. Safety and tolerability data will be summarized by treatment or by treatment sequence and overall, where applicable.

Frequency counts (number of subjects [n] and percentages) will be made for each qualitative variable. Descriptive statistics (n, mean, standard deviation [SD], median, minimum and maximum) will be calculated for each quantitative variable (unless otherwise stated). Descriptive statistics will only be presented if  $n \geq 3$ .

The following rules will apply to any repeated safety assessments occurring within each treatment period:

- If the repeated measurement of a specific parameter occurs prior to IMP administration (Day 1), then the last obtained value prior to dosing will be used in the descriptive statistics and in the calculation of changes from baseline;
- If the repeated measurement of a specific parameter occurs after IMP administration (Day 1), then the first (non-missing) value after dosing will be used in descriptive statistics and in the calculation of changes from baseline.

The planned sequence for measurement of multiple assessments at the same time point is described in [Section 7.3](#).

For safety assessments performed at screening and the final follow-up, the following rules will apply for any repeated assessments:

- If the repeated assessment occurs at screening the last available value will be used in the summary statistics;
- If the repeated assessment occurs at the final follow-up visit the first non-missing assessment will be used in the summary statistics.

All statistical analyses and production of tables, figures and listings will be performed using SAS® version 9.2 or later.

#### **11.2.1. Missing Data**

Missing dates and times in the AE data will be handled as described in [Section 11.10.1](#). Concentrations that are below limit of quantification (BLQ) in the PK data will be handled as described in [Section 11.9.2](#).

There will be no imputations of other missing data. All subjects will be included into the safety analyses as far as the data permit.

### **11.3. Study populations**

#### **11.3.1. Safety analysis set**

The safety analysis set will include all subjects who received at least one dose of naloxegol and for whom any safety post-dose data are available.

Unless otherwise stated the safety analysis set will be used for the presentation of all demographic and disposition data, as well as all safety analyses. Exposure to IMP will also be presented using the safety analysis set.

#### **11.3.2. Pharmacokinetic analysis set**

The PK analysis set will be a subset of those subjects in the safety analysis set and will include subjects who received at least one dose of IMP and had at least one post-dose plasma concentration measurement at a scheduled time-point without important protocol deviations or violations thought to significantly affect the PK (e.g., subject vomited, wrong dose administered, prohibited concomitant medication taken).

Data from subjects may be excluded from the PK analysis set as a result of the following:

- Subjects who experienced vomiting at or before 2 x median  $t_{max}$  will be excluded for the affected treatment period

Following oral administration, naloxegol is absorbed at less than 2 hours [4].

- Subjects whose pre-dose plasma naloxegol concentration is > 5% of the corresponding  $C_{max}$  will be excluded for the specific treatment period

A subject may be excluded from the analysis only for the specific treatment period in which the AE occurred.

The exclusion of any subjects or concentrations at certain time-points from the calculation of the PK parameters will be documented by the PK Scientist including the reason(s) for exclusion.

The concentration data and PK parameter data for subjects excluded from the PK analysis set will be listed only.

#### **11.4. Determination of sample size and statistical considerations**

Based on Study D3820C00018, the intra-subject coefficient of variation percentage (CV%) = 15.7% for  $C_{max}$  and 31.9% for AUC. Thirty-six subjects (9 subjects per sequence) are needed to provide at least 80% power to show that the 90% confidence interval (CI) of the ratio for a specific parameter ( $C_{max}$  and AUC) of each test formulation of naloxegol compared to the whole tablet (reference) formulation is within 0.80 and 1.25. This calculation is based on a CV of 31.9% and an expected mean ratio of 1.00. No multiplicity adjustment is planned.

Up to 44 subjects will be randomized to a 4 sequence Williams design for 4 periods and 4 treatments: ADBC, BACD, CBDA and DCAB, in order to ensure at least 36 evaluable subjects at the end of the last treatment period.

#### **11.5. Protocol deviations**

Protocol deviations are considered any deviation from the clinical study protocol relating to a subject, and include the following:

- Inclusion/exclusion criteria deviations
- Dosing deviations (e.g., incorrect treatment received, subject was not fasted as per the protocol requirements prior to and after dosing)
- Time window deviations for safety and/or PK assessments
- Subjects receiving prohibited concomitant medications

- Other procedural and study conduct deviations recorded by the clinical unit on a protocol deviation log

The criteria for the assessment and reporting of protocol deviations will be stipulated in a separate study-specific protocol deviation specification (PDS) document. This will include a Windows Allowance Document (WAD) which stipulates tolerance windows for safety and PK assessments. Measurements performed within these tolerance windows will not be considered as protocol deviations and will not be reported.

All protocol deviations will be discussed at the data review meeting prior to database hard lock in order to define the analysis sets for the study.

Protocol deviations will be listed by subject.

Protocol deviations will be handled in accordance with PAREXEL SOPs.

For handling of protocol amendments, see [Section 3.6](#).

#### **11.6. Subject disposition**

Subjects and/or data excluded from the PK analysis set will be listed including the reason for exclusion. Subject disposition will be summarized by treatment sequence and overall, and will include the following information: number of subjects randomized and dosed, number and percentage of subjects completing the study and the number and percentage of subjects who were withdrawn (including reasons for withdrawal). Disposition data will be presented for all randomized subjects.

Subject discontinuations will be listed including the date of study exit, duration of treatment and reason for discontinuation. A listing of informed consent response will also be presented.

#### **11.7. Demographic and baseline data**

Demographic variables (age, gender, race, ethnicity, height, weight and BMI) will be listed by subject. Demographic characteristics (age, gender, race and ethnicity) and subject characteristics (height, weight and BMI) will be summarized separately by treatment sequence and for all subjects. The denominator for percentages will be the number of subjects in the safety analysis set for each treatment sequence or for all subjects as applicable.

Medical history data will be listed by subject including visit, description of the disease/procedure, Medical Dictionary for Regulatory Activities (MedDRA) System Organ Class (SOC), MedDRA preferred term (PT), start date, and stop date (or ongoing if applicable).

A summary of the number and percentage of subjects who had relevant medical histories will be presented by treatment sequence and for all subjects for the medical history PT.

## **11.8. Prior and concomitant medication and drug administration**

### **11.8.1. Prior and concomitant medication**

Prior medications are those that started and stopped prior to the first dose of IMP; all medications taken after first dosing are considered as concomitant (including medications that started prior to dosing and continued after).

Prior and concomitant medication will be listed by subject and will include the following information: reported name, PT, the route of administration, dose, frequency, start date/time, duration and indication. Prior and concomitant medication will be coded according to the sponsor's drug dictionary.

### **11.8.2. Drug administration**

Drug administration dates and times, including volume administered (where applicable) will be listed for each subject and treatment period.

## **11.9. Pharmacokinetic analysis**

### **11.9.1. Pharmacokinetic parameters**

Where possible, the following PK parameters will be calculated for naloxegol.

#### **Primary PK parameters**

AUC	Area under plasma concentration-time curve from time zero extrapolated to infinity
AUC (0-t)	Area under the plasma concentration-time curve from time zero to time of last quantifiable concentration
C max	Observed maximum plasma concentration

#### **Secondary PK parameters**

t max	Time to reach maximum plasma concentration
t 1/2λz	Half-life associated with terminal slope (λ z ) of a semi-logarithmic concentration-time curve
MDT	Mean dissolution time (whole tablet only) (calculated as MRT Treatment D [Reference] – MRT Treatment C [Test] )
MRT	Mean residence time
λ z	Terminal elimination rate constant

---

CL/F	Apparent total body clearance after extravascular administration estimated as dose divided by AUC
$V_z$ /F	Apparent volume of distribution during the terminal phase after extravascular administration

The following diagnostic parameters for plasma PK analysis will be listed, but not summarized:

$\lambda_z$ upper and lower	The time interval (h) of the log-linear regression to determine $t_{1/2}$
$\lambda_z, N$	Number of data points included in the log-linear regression analysis
Rsq_adj	Regression coefficient adjusted for $\lambda_z, N$ , Goodness of fit statistic for calculation of $\lambda_z$
%AUC extr	Percentage of AUC obtained by extrapolating the area under the plasma concentration-time curve to infinity from the time of the last quantifiable plasma concentration using $\lambda_z$

Additional PK parameters may be determined where appropriate.

### 11.9.2. Derivation of Pharmacokinetic Parameters

The PK analyses of the plasma concentration data for naloxegol will be performed by Covance, on behalf of Clinical Pharmacokinetic Alliance, AstraZeneca Research and Development.

PK parameters will be derived using non-compartmental methods with Phoenix® WinNonlin® Version 6.3, or higher and/or SAS® Version 9.2, or higher. All descriptive and inferential statistical computations will be performed using SAS® Version 9.2, or higher.

PK analysis will, where possible, be carried out using actual times recorded in the raw data. If actual times are missing, nominal times will be used.

Plasma concentrations which are BLQ prior to the first quantifiable concentration will be set to a value of zero. After the first quantifiable concentration, any BLQ plasma concentrations will be set to missing for all concentration profiles. Where two or more consecutive concentrations are BLQ at the end of a profile, the profile will be deemed to have terminated and therefore any further quantifiable concentrations will be set to missing for the calculation of the PK parameters unless it is considered to be a true characteristic of the profile of the drug.

If an entire concentration-time profile is BLQ, the profile will be excluded from the PK analysis.

Terminal elimination half-life is estimated as  $(\ln 2)/\lambda_z$ , where  $\lambda_z$  refers to the terminal elimination rate constant, estimated by log-linear least squares regression of the terminal part of the concentration-time curve. For the determination of  $\lambda_z$ , the start of the terminal elimination phase for each subject will be defined by visual inspection and will be the first point at which there is no systematic deviation from the log linear decline in plasma concentrations. A minimum of 3 data points will be used in calculating  $\lambda_z$ , and the duration of time over which PK blood samples were collected will be at least twice the subsequently estimated terminal half-life. Where an elimination half-life is estimated to be more than half of the PK collection interval, it will be flagged, commented upon in the study report and interpreted with caution. AUC is estimated by  $AUC_{(0-t)} + C_{last}/\lambda_z$  where  $C_{last}$  is the observed last quantifiable drug concentration. AUC values where the percentage extrapolation is less than 20% will be reported. The AUC values where the percentage extrapolation is greater than 20% will be flagged in the data listings.

AUCs (including AUC and  $AUC_{(0-t)}$ ) will be calculated using the linear trapezoidal method when concentrations are increasing and the logarithmic trapezoidal method when concentrations are decreasing.

The minimum requirement for the calculation of AUC will be the inclusion of at least three consecutive plasma concentrations above the lower limit of quantification (LLOQ), with at least one of these concentrations following  $C_{max}$ .

### 11.9.3. Presentation of pharmacokinetic data

A listing of PK blood sample collection times, as well as derived sampling time deviations will be provided. Plasma concentrations and PK parameters will be summarized by treatment (where treatments will be pooled across treatment periods) using appropriate descriptive statistics. Where possible, the following descriptive statistics will be presented: n, geometric mean, geometric CV, arithmetic mean, arithmetic SD, median, minimum and maximum. For  $t_{max}$ , only n, median, minimum and maximum will be presented.

The geometric mean is calculated as the exponential of the arithmetic mean calculated using log-transformed data.

The CV% is calculated as  $100 \cdot \sqrt{(\exp(s^2) - 1)}$  where  $s$  is the SD of the log-transformed data.

For concentration data the mean, geometric mean, SD, median, minimum and maximum values will be reported to three significant figures and CV% to one decimal place. Individual

PK parameters will be presented to three significant figures, with the exception of  $t_{\max}$  which will be presented to two decimal places. Values >1000 in either the concentration data or PK parameter data will be presented to the nearest integer.

Plasma concentrations that are BLQ or if there are missing values (e.g., no result [NR]) will be handled as follows:

- Where there is NR, these will be set to missing.
- At a time-point where less than or equal to 50% of the values are BLQ, all BLQ values will be set to the LLOQ, and all descriptive statistics will be calculated.
- At a time-point where more than half of the values are BLQ, the mean, SD, geometric mean and CV% will be set to Not Determined (ND). The max value will be reported from the individual data, and the min and median will be set to BLQ.
- If all values are BLQ at a time-point, no descriptive statistics will be calculated for that time-point. Not applicable (NA) will be written in the field for standard deviation and CV% and BLQ will be written in fields for mean, geometric mean, min, median, and max.
- The number of BLQ values (n below LLOQ) will be reported for each time-point.

Data from subjects excluded from the PK analysis set will be included in the data listings, but not in the descriptive statistics or in the inferential statistics.

Individual plasma concentrations versus actual time will be plotted in linear and semi logarithmic scale with all treatments overlaid on the same plot and separate plots for each subject.

Combined individual plasma concentration versus actual times will be plotted in linear and semi logarithmic scale. Plots will be grouped by treatment.

Arithmetic mean plasma concentration ( $\pm$ SD) versus nominal sampling time will be plotted in linear and semi logarithmic (no SD presented) scale with all treatments overlaid on the same figure.

For mean plots, BLQ values will be handled as described for the summary tabulations; for individual plots plasma concentrations which are BLQ prior to the first quantifiable concentration will be set to a value of zero (linear plots only). After the first quantifiable concentration, any BLQ plasma concentrations will be regarded as missing. All individual and mean plots will be based on the PK analysis set.

#### **11.9.4. Statistical analysis**

Analyses will be performed using a linear analysis of variance (ANOVA) model using the natural logarithm of AUC,  $AUC_{(0-t)}$  and  $C_{max}$  as the response variables and fixed effects of sequence, period, treatment and subject nested within sequence.

Transformed back from the logarithmic scale, geometric least squares means together with 2-sided 95% CIs along with CV for AUC,  $AUC_{(0-t)}$  and  $C_{max}$  will be estimated and presented. Also, ratios of geometric means for AUC,  $AUC_{(0-t)}$  and  $C_{max}$  (each test treatment compared to the reference naloxegol tablet formulation) together with CIs (2-sided 90%) will be estimated and presented.

Data from healthy subjects excluded from the PK analysis set will be included in the data listings, but not in the summaries or statistical analyses.

The statistical analysis will be conducted separately for the following:

- Treatment A versus Treatment D
- Treatment B versus Treatment D
- Treatment C versus Treatment D

Only the data for the comparison under investigation will be included in the statistical analysis i.e., when comparing Treatment A and Treatment D, the data for Treatment B and Treatment C will be removed from the dataset.

Subjects must have the specific PK parameter (i.e., AUC,  $AUC_{(0-t)}$  or  $C_{max}$ ) available for both treatments of naloxegol in order to be included in a specific relative bioavailability assessment; a subject may therefore be included in one, two or all comparisons for each of the PK parameters.

In this analysis no adjustments will be made for multiple comparisons.

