### **Pharmacokinetic data analysis**

The PK analysis set will be a subset of those subjects in the safety analysis set and will include subjects who received at least one dose of IMP and had at least one post-dose plasma concentration measurement at a scheduled time-point without important protocol deviations or violations thought to significantly affect the PK (e.g., subject vomited, wrong dose administered, prohibited concomitant medication taken).

Analyses will be performed using a linear analysis of variance (ANOVA) model with the natural logarithm of AUC,  $AUC_{(0-t)}$  and  $C_{max}$  as the response variables and fixed effects of sequence, period, treatment and subject nested within sequence.

Transformed back from the logarithmic scale, geometric least squares means together with 2-sided 95% confidence intervals (CIs) and coefficient of variation (CV) for AUC,  $AUC_{(0-t)}$  and  $C_{max}$  will be estimated and presented. Also, ratios of geometric means for AUC,  $AUC_{(0-t)}$  and  $C_{max}$  (each test treatment compared to the reference naloxegol tablet formulation) together with CIs (2-sided 90%) will be estimated and presented.

The concentration data and PK parameter data for subjects excluded from the PK analysis set will be listed only.

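### The 95% CIs for the geometric LS means come from a fixed-subject ANOVA, so they leave out between-subject variance and are too narrow for a population mean

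*Protocol*

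**What the plan says.** Section 11.9.4 specifies a linear ANOVA on the natural logarithms of AUC, AUC(0-t) and Cmax, with "fixed effects of sequence, period, treatment and subject nested within sequence". No term is random. Two kinds of result are taken from this model:

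- "geometric least squares means together with 2-sided 95% CIs along with CV", back-transformed;
- ratios of geometric means, "each test treatment compared to the reference naloxegol tablet formulation", with 2-sided 90% CIs.

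The model is fitted separately for A/D, B/D and C/D: "Only the data for the comparison under investigation will be included in the statistical analysis". A subject must have the parameter "available for both treatments of naloxegol in order to be included in a specific relative bioavailability assessment", so each model holds complete pairs. The synopsis (Pharmacokinetic data analysis) specifies the same model and the same two outputs.

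Neither place gives another method for the LS-mean intervals or says that they are conditional on the volunteers studied. Section 11.1 says that no separate SAP will be written, apart from a possible abbreviated one to record changes. Section 11.9.4 is therefore the working specification.

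**The concern.** When subject is fixed, the only error term is the within-subject residual. That is the right error for a difference between two treatments in the same person, so the model suits the ratios. It is the wrong error for the level of exposure under one treatment. The interval then answers what the mean would be if these same volunteers were dosed again, and not what the mean is in the population they were drawn from.

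The protocol itself gives reason to expect real between-subject variance. Section 5.4.5 reports that exposure rises with body weight and that AUC differs by about 20% between race groups, and section 7.6.1 admits subjects from 50 to 100 kg.

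At stake are the intervals on mean exposure for each method of administration, for all three primary PK parameters. Section 11.9.3 plans no other confidence interval on treatment-level exposure. A reader who compares these means with another study would take them to be more precise than they are.

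**Working it through.** **Inputs**
- n = 36 evaluable, 9 per sequence (section 11.4); sequences ADBC, BACD, CBDA, DCAB.
- Within-subject CV (section 11.4): "intra-subject coefficient of variation percentage (CV%) = 15.7% for" Cmax, and 31.9% for AUC.
- Between-subject CV: not in the protocol. Assumed range 20% to 60%.

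**Reproducing the protocol's own figure.** For sizing, section 11.4 says: "This calculation is based on a CV of 31.9% and an expected mean ratio of 1.00". With σ_w = √ln(1 + CV²), SE = σ_w√(2/n), limits 0.80 to 1.25 and two one-sided 5% tests, n = 36 gives 83.1% power for the full 4×4 model (df 3n − 6) and 81.8% or 81.7% for a pairwise model (df n − 2 or n − 4). The smallest n for 80% is 34 or 35, and the next multiple of 4 is 36. The sample size reproduces.

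**Variance of the LS mean.** The fixed-effects design matrix was built for each of the A/D, B/D and C/D data sets. In all three, the LS mean is estimable and
- model variance of an LS mean = σ_w²/36 (factor 0.02778), with no between-subject part;
- model variance of the treatment difference = 2σ_w²/36 (factor 0.05556).

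Over repeated samples of subjects, the true variance of the LS mean is (σ_w² + σ_b²)/36.

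**Numbers**
- AUC: σ_w² = ln(1 + 0.319²) = 0.0969, so model SE = √(0.0969/36) = 0.0519.
- Cmax: σ_w² = ln(1 + 0.157²) = 0.0244, so model SE = √(0.0244/36) = 0.0260.
- Example, AUC at between-subject CV 40%: σ_b² = ln(1.16) = 0.1484; true SE = √((0.0969 + 0.1484)/36) = 0.0826; ratio 0.0826/0.0519 = 1.59.

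**Coverage.** The residual mean square does not contain the subject effects, so coverage = P(|T| ≤ t/r). Here T has 32 df (A/D and C/D; 33 for B/D), t = 2.037, and r is the ratio of true to model SE. For AUC at 40%, 2.037/1.59 = 1.28, which gives 79.0%.

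| Between-subject CV (assumed) | AUC: true SE | r | Coverage | Cmax: true SE | r | Coverage |
|---|---|---|---|---|---|---|
| 20% | 0.0615 | 1.19 | 90.5% | 0.0420 | 1.62 | 78.3% |
| 30% | 0.0713 | 1.37 | 85.2% | 0.0554 | 2.13 | 65.4% |
| 40% | 0.0826 | 1.59 | 79.0% | 0.0693 | 2.66 | 55.0% |
| 50% | 0.0943 | 1.82 | 72.9% | 0.0829 | 3.19 | 47.3% |
| 60% | 0.1060 | 2.04 | 67.4% | 0.0960 | 3.69 | 41.5% |

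Simulation of the A/D model (40,000 trials per setting) agrees to within half a percentage point. In the same runs the 90% CI of the ratio covered between 89.5% and 90.2%.

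**Width on the original scale**, at a between-subject CV of 40%. For AUC the upper limit lies exp(2.037 × 0.0519) = 1.111 times the geometric mean under the protocol's model, and exp(2.037 × 0.0826) = 1.183 times with between-subject variance included. For Cmax the factors are 1.054 and 1.152.

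**Fixed against random subject on one simulated data set** (between-subject CV 40%, within-subject 31.9%). The SE of the LS mean was 0.053 with subject fixed and 0.084 with subject random. The SE of the treatment difference was 0.0748 both ways.

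**The case against.** The algebra is hard to dispute, so the case on the other side concerns weight.

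- **No objective or decision uses these intervals.** The primary objective is relative bioavailability, and the sample size and the 0.80 to 1.25 limits concern only the 90% CI of the ratio. This stands, and it confines the consequence to descriptive output.
- **Total variability is reported elsewhere.** Section 11.9.3 plans n, the geometric mean and a geometric CV based on the SD of the log data, which contains both variance components. A reader could build a proper interval from these. This also stands, but it does not make the published interval correct. It puts a table showing total variability beside intervals that ignore part of it.
- **The interval is valid conditional on these subjects, and the protocol never claims population coverage.** True, but the protocol does not state the conditioning either. A 95% CI for a mean exposure with no label will be read as a statement about the population. A label would be the smallest adequate repair.
- **The size rests on an assumed between-subject CV.** It does. At 20%, AUC coverage is about 90.5%, a modest loss. The lowest figure, 41.5%, belongs to Cmax at 60%. The direction needs no assumption beyond a between-subject variance above zero.

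**Conclusion.** The concern holds. As specified, the 95% CIs of the geometric LS means carry only within-subject error and cover the population geometric mean less than 95% of the time. With 36 complete subjects and the protocol's within-subject CVs, coverage falls from about 91% to 67% for AUC and from about 78% to 41% for Cmax as the assumed between-subject CV goes from 20% to 60%. Confidence is high in the direction. The size depends on a between-subject CV that the protocol does not give.

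The bioequivalence conclusion does not change. The fixed-subject ANOVA is sound for the ratios and their 90% CIs, and the sample size stands. The correction should be made because these are prespecified intervals on all three primary PK parameters, but it does not threaten the study's main result.

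**What to change.** In section 11.9.4 and the synopsis, keep the fixed-subject ANOVA for the test/reference ratios and their 90% CIs. Add one sentence that the geometric LS means and their 95% CIs come from the same model with subject(sequence) as a random effect, fitted by REML. A t-interval per treatment on the log-transformed values is an acceptable alternative. If neither is wanted, state in the text and table footnotes that the 95% CIs are conditional on the subjects studied and reflect within-subject variability only.

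The cost is one sentence in two places and one extra model statement. The reported 95% CIs become wider. The ratios, their 90% CIs and the sample size do not change.
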